7.3. Variables

The following variables will be assessed at index date

- Demographic characteristics
 - Age (years)
 - Sex assigned at birth
 - Gender (trans, cis)
 - Race (African American/Black, Asian, White, Other Race)
 - Ethnicity (Hispanic, non-Hispanic)
 - Geographic Region (Northeast, Midwest, South, West, US Territories)
 - Marital status
 - Payer type (Medicaid, Medicare, Commercial insurance, Cash)
- Clinical characteristics
 - Time since first OPERA visit
 - Number of visits with OPERA healthcare provider (HCP) within 12 months prior to baseline
 - Prescriber specialty (MD or DO, physician associate, nurse practitioner, other/unknown)
 - Clinic type (healthcare center, wellness center, other)
- Sexual Behavior and Health
 - History of STI (ever)
 - a) Syphilis
 - b) Gonorrhea

ⁱ The CDC PrEP Clinical Practice Guideline recommends using an STI in the past 6 months as an indication for PrEP. This has been extended to an STI in the past 12 months for this protocol.

ⁱⁱ The National HIV/AIDS Strategy for the United States 2022–2025 identifies youth aged 12-24 as a priority population. This has been changed to individuals aged 18-24 in accordance with the study inclusion criteria Protocol for Non-Interventional Studies PASS Studies and Non-PASS Studies (4.0) March 2024

Template Doc ID: TMF-15706807

Parent Doc ID: VQD-SOP-066694

- c) Chlamydia
- d) Chancroid
- e) Lymphogranuloma venereum
- f) *Mycoplasma genitalium*
- g) Herpes Simplex-2 (HSV-2) infection
- h) Trichomoniasis infection
- i) Human papilloma virus (HPV)/genital warts
- o History of STI (past 3 months)
 - a) Syphilis
 - b) Gonorrhea
 - c) Chlamydia
 - d) Chancroid
 - e) Lymphogranuloma venereum
 - f) *Mycoplasma genitalium*
 - g) HSV-2
 - h) Trichomoniasis infection
 - i) HPV/genital warts

7.3.1. Exposure definitions

People without HIV in OPERA (Obj 1)

Not applicable

People with a new HIV diagnosis (Obj 1.a)

PrEP use (never, use within ≤ 12 months before diagnosis, use > 12 months before diagnosis)

- Formulation (TDF/FTC, TAF/FTC, CAB LA)
- Number of PrEP formulations
- Presence and duration of gaps without PrEP use

PrEP users (Obj 2-5)

Time-updated PrEP type (oral or LA).

People who could benefit from PrEP (Obj 6)

Not applicable

7.3.2. Outcome definitions

People without HIV in OPERA (Obj 1)

Incident HIV diagnosis

- New HIV diagnosis and/or detectable HIV RNA and/or positive antigen/antibody test
- All potential incident HIV diagnoses will be subject to a thorough chart review for confirmation

People with a new HIV diagnosis (Obj 1.a)

Not applicable

Protocol for Non-Interventional Studies PASS Studies and Non-PASS Studies (4.0) March 2024

Template Doc ID: TMF-15706807

Parent Doc ID: VQD-SOP-066694

PrEP users (Obj 2-5)

Incident HIV diagnosis

- Frequency of new HIV diagnosis and/or detectable HIV RNA and/or positive antigen/antibody test
- Months from start of PrEP type (oral vs. LA) to HIV diagnosis
- Rate of incident HIV diagnoses per 100 person-years of follow-up
 - Within the first 12 months after index PrEP start
 - Through study end (Analysis #1: 30JUN2024; Analysis #2: 30JUN2025)
 - Follow-up (FU) will be censored at first of:
 - HIV diagnosis
 - Death
 - Study end (Analysis #1: 30JUN2024; Analysis #2: 30JUN2025)
 - Loss to follow-up (12 months after last clinical contact)
 - 12 months after index date
- All potential HIV acquisitions will be subject to a thorough chart review for confirmation
 - All lab results, diagnoses, ART prescriptions and clinician notes available in OPERA on or after the potential HIV acquisition was identified will be reviewed

PrEP coverage

- Oral PrEP coverage:
 - Proportion of days of access to oral PrEP in the 12-months following index PrEP initiation
 - Follow-up (FU) will be censored at first of:
 - a) Death
 - b) Study end (Analysis #1: 30JUN2024; Analysis #2: 30JUN2025)
 - c) Loss to follow-up (12 months after last clinical contact)
 - d) 12 months after index date
 - Access to oral PrEP will be determined based on the dates and days of supply for each prescription (e.g., a prescription for 30 pills/month with 3 refills provides 90 days of access)
 - a) Each calendar day will only be counted once, even if there is an overlap between access from the prior prescription and start of the next prescription.

$$\% \text{ access} = \frac{\sum \text{Number of pills in each prescription}}{\text{Number of FU days}} \times 100\%$$

- LA PrEP coverage:
 - Proportion of days of coverage by CAB LA over follow-up
 - Follow-up (FU) will be censored at first of:
 - a) Death
 - b) Study end (Analysis #1: 30JUN2024; Analysis #2: 30JUN2025)

- c) Loss to follow-up (12 months after last clinical contact)
- d) 12 months after index date
- Coverage by LA PrEP will be determined based on the duration of medication from injection date forward. The number of days of coverage per injection were derived from the CAB LA PrEP USPI label.¹⁴
 - 1st injection: coverage = 37 days (30 days of coverage + 7-day injection window)
 - Subsequent injections: coverage = 67 days (60 days of coverage + 7-day injection window)
 - Each calendar day will only be counted once, even if there is an overlap between coverage from the prior injection and date of the next injection.

$$\% \text{ coverage} = \frac{\sum \min(\text{coverage, days between injections})}{\text{Number of FU days}} \times 100\%$$

HIV testing & STI screening

- HIV testing
 - Assessed within 14 days before PrEP start and over the first 12 months after PrEP start
 - Frequency and rate (per 100 person years) of HIV tests over 12-month period
 - Type of HIV tests (RNA [quantitative, qualitative], antigen/antibody, rapid screen)
 - Timing of HIV tests as recommended by PrEP clinical guidelines⁷
 - Oral PrEP: on-schedule testing defined as receiving an HIV test ≤14 days before/at start, and 3 months (76-104 days) after each test
 - LA PrEP: on-schedule testing defined as receiving an HIV test ≤14 days before/at first injection, and ±14 days of each subsequent injection
 - HIV testing practices (type, frequency) by type of healthcare provider (MD or DO, physician associate, nurse practitioner, other/unknown)
 - HIV testing practices (type, frequency) by clinic type (healthcare center, wellness center, other)
- STI screening
 - Assessed within 14 days before PrEP start and over the first 12 months after PrEP start
 - Frequency and rate (per 100 person years) of STI testing events (testing for multiple STIs on the same day will count as 1 testing event)
 - Type of other STI tests
 - Syphilis
 - Gonorrhea
 - Chlamydia
 - Chancroid
 - Lymphogranuloma venereum

- Mycoplasma genitalium
- Hepatitis B virus (HBV)
- Hepatitis C virus (HCV)
- HSV-2
- Trichomoniasis
- HPV and/or genital warts
- Timing of STI tests as recommended by PrEP clinical guidelines⁷
 - Testing 3 months (76-104 days) after last test
 - Testing 6 months (168-196 days) after last test
 - Testing 12 months (351-379 days) after last test
- STI screening practices (type, frequency) by type of healthcare provider (MD or DO, physician associate, nurse practitioner, other/unknown)
- STI screening practices (type, frequency) by clinic type (healthcare center, wellness center, other)
- Crosstabulation of HIV and STI testing frequency
- STI diagnoses
 - New diagnosis of STI as noted in medical record or positive test result
 - STI diagnoses for
 - Syphilis
 - Gonorrhea
 - Chlamydia
 - Chancroid
 - Lymphogranuloma venereum
 - Mycoplasma genitalium
 - Hepatitis B virus (HBV)
 - Hepatitis C virus (HCV)
 - HSV-2
 - Trichomoniasis
 - HPV and/or genital warts

People who could benefit from PrEP (Obj 6)

HIV testing & STI screening

- HIV testing
 - Frequency and rate (per 100 person years) of HIV tests over 12-month period
 - Type of HIV tests (RNA [quantitative, qualitative], antigen/antibody, rapid screen)
 - HIV testing practices (type, frequency) by HCP type (MD or DO, physician associate, nurse practitioner, other/unknown)
 - HIV testing practices (type, frequency) by clinic type (healthcare center, wellness center, other)
- HIV diagnoses
 - Frequency of new HIV diagnosis and/or detectable HIV RNA and/or positive antigen/antibody test
 - Rate of incident HIV diagnoses per 100 person-years of follow-up
 - Within the first 12 months after index PrEP start
 - Through study end (Analysis #1: 30JUN2024; Analysis #2: 30JUN2025)

- Follow-up (FU) will be censored at first of:
 - HIV diagnosis
 - Death
 - Study end (Analysis #1: 30JUN2024; Analysis #2: 30JUN2025)
 - Loss to follow-up (12 months after last clinical contact)
 - 12 months after index date
- All potential HIV acquisitions will be subject to a thorough chart review for confirmation
 - All lab results, diagnoses, ART prescriptions and clinician notes available in OPERA on or after the potential HIV acquisition was identified will be reviewed
- STI screening
 - Frequency and rate (per 100 person years) of STI testing events (testing for multiple STIs on the same day will count as 1 testing event)
 - Type of other STI tests
 - Syphilis
 - Gonorrhea
 - Chlamydia
 - Chancroid
 - Lymphogranuloma venereum
 - Mycoplasma genitalium
 - Hepatitis B virus (HBV)
 - Hepatitis C virus (HCV)
 - HSV-2
 - Trichomoniasis
 - HPV and/or genital warts
 - Timing of STI tests as recommended by PrEP clinical guidelines⁷
 - Testing 3 months (76-104 days) after last test
 - Testing 6 months (168-196 days) after last test
 - Testing 12 months (351-379 days) after last test
 - STI screening practices (type, frequency) by HCP type type (MD or DO, physician associate, nurse practitioner, other/unknown)
 - STI screening practices (type, frequency) by clinic type (healthcare center, wellness center, other)
- Crosstabulation of HIV and STI testing frequency
- STI diagnoses
 - New diagnosis of STI as noted in medical record or positive test result
 - STI diagnoses for
 - Syphilis
 - Gonorrhea
 - Chlamydia
 - Chancroid
 - Lymphogranuloma venereum
 - Mycoplasma genitalium
 - Hepatitis B virus (HBV)
 - Hepatitis C virus (HCV)
 - HSV-2

- Trichomoniasis
- HPV and/or genital warts

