7. RESEARCH METHODS

7.1. Study Design

A cohort study using secondary data from the OPERA[®] (Observational Pharmacology Epidemiology Research & Analysis) cohort will be used to answer the study objectives. OPERA is a multi-site observational database collecting data prospectively from the complete electronic health records (EHR) from clinical care throughout the US.

[figure not shown]
Analyses to meet the study objectives will be conducted twice during the study period. Analysis #1 will include data from 01JAN2021-31DEC2023 (Obj. 1-1a) and from 21DEC2021 to 30JUN2024 (Obj 2-6). Analysis #2 will be a repeat of Analysis #1 with data from 1JAN2021-31DEC2024 (Obj. 1-1a) and from 21DEC2021 to 30JUN2025 (Obj 2-6). A

summary of the study design is provided in Table 1 (exposure groups, index date, censoring criteria, endpoints) and in Figure 1 (timeline).

Table 1. Summary of study design

		Analysis #1	Analysis #2
Obj 1 Among all people without HIV in OPERA	Exposure groups	Calendar years	Calendar years
	Index date	NA	NA
	Censoring criteria	NA	NA
	Endpoints	HIV diagnosis	HIV diagnosis
Obj 1a Among people with a new HIV diagnosis	Exposure groups	PrEP use (never, use within ≤12 months before diagnosis, use >12 months before diagnosis)	PrEP use (never, use within ≤12 months before diagnosis, use >12 months before diagnosis)
	Index date	Date of HIV diagnosis	Date of HIV diagnosis
	Censoring criteria	NA	NA
	Endpoints	NA	NA
Obj 2-5 Among PrEP users	Exposure groups	Oral PrEP, CAB LA PrEP	Oral PrEP, CAB LA PrEP
	Index date	Start of first PrEP regimen during the study period	Start of first PrEP regimen during the study period
	Censoring criteria	Death, loss to follow-up (12 months after last clinical contact), study end (30JUN2024), 12 months after index date	Death, loss to follow-up (12 months after last clinical contact), study end (30JUN2025), 12 months after index date
	Endpoints	HIV diagnosis, PrEP coverage, HIV testing, STI screening, STI diagnoses	HIV diagnosis, PrEP coverage, HIV testing, STI screening, STI diagnoses
Obj 6 Among people who could benefit from PrEP	Exposure groups	NA	NA
	Index date	First OPERA visit with indication for PrEP during study period	First OPERA visit with indication for PrEP during study period
	Censoring criteria	Death, loss to follow-up, study end (30JUN2024), 12 months after index date, PrEP initiation	Death, loss to follow-up, study end (30JUN2025), 12 months after index date, PrEP initiation

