7.2. Study Population and Setting

7.2.1. Inclusion Criteria

People without HIV in OPERA (Obj 1)

- i. ≥ 1 clinical encounter in OPERA during the calendar year of interest
- ii. ≥ 18 years old at the first clinical encounter during the calendar year of interest
- iii. No evidence of prior HIV diagnosis

People with a new HIV diagnosis (Obj 1.a)

- i. Incident HIV diagnosis (new HIV diagnosis/positive HIV test/detectable HIV RNA viral load) identified in Obj 1

PrEP users (Obj 2-5)

- i. HIV-negative
- ii. ≥ 18 years of age
- iii. Started any new PrEP formulation
 - Analysis #1: between 21DEC2021 and 30JUN2023
 - Analysis #2: between 21DEC2021 and 30JUN2024
- iv. With or without prior PrEP use (a different formulation or a gap ≥ 61 days without any PrEP immediately prior to the index PrEP; the same formulation may have been used ≥ 61 days before starting the index PrEP)

People who could benefit from PrEP (Obj 6)

- i. HIV-negative
- ii. ≥ 18 years of age

- iii. ≥ 1 clinical encounter in OPERA during the inclusion period
 - Analysis #1: between 21DEC2021 and 30JUN2023
 - Analysis #2: between 21DEC2021 and 30JUN2024
- iv. Any of the following indications for PrEP¹¹:
 - Bacterial STI in past 12 monthsⁱ (gonorrhea, syphilis, chlamydia)⁷
 - Alcohol use disorder⁷
 - Illicit non-injection drug use⁷
 - Injection drug use^{7, 14}
 - Black women¹⁴
 - Transgender women¹⁴
 - Men who have sex with men¹⁴
 - All individuals aged 18-24 yearsⁱⁱ¹⁴
 - Any history of PrEP use

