7.7.1. Primary analysis

7.7.1.1. Main Analytical approach

People without HIV in OPERA (Obj 1)

For each calendar year, the number and percentage of new HIV diagnoses will be reported out of all individuals receiving care at an OPERA clinic.

People with a new HIV diagnosis (Obj 1.a)

Among newly diagnosed people with HIV, PrEP use (never, use within ≤ 12 months before diagnosis, use > 12 months before diagnosis) and PrEP characteristics will be described using counts and proportions for categorical variables and median and interquartile ranges for continuous variables.

PrEP users (Obj 2-5)

(Obj 2) Baseline demographic and clinical characteristics will be described at the start of PrEP use during the study period, by regimen type (oral or LA), using median and interquartile ranges for continuous variables and counts and proportions for categorical variables.

Individuals contributing to both the oral and CAB LA PrEP groups may be included in both groups.

(Obj 3) The number, percentage, and incidence rate (per 100 person-years) of incident HIV diagnoses within 12 months of starting index PrEP and through study end will be described by route of administration (time-updated, oral or LA). The timing of HIV testing relative to PrEP start and HIV diagnosis will be described to assess to possibility of attributing HIV acquisition to the correct PrEP type. Incidence rates of HIV diagnoses (per 100 person-years) within 12 months of start and through study end will be estimated using time-updated univariate Poisson regression for each regimen type (time-updated, oral vs LA) to account for varying duration of follow-up.

(Obj 4) The percentage of days with access to oral PrEP and the percentage of days with coverage by CAB LA PrEP will be described over the first 12 months after index PrEP initiation.

(Obj 5) The frequency and rate (per 100 person-years) of HIV testing, STI screening, and STI diagnoses at index PrEP initiation and in the 12-months after index PrEP initiation.

Characteristics of the tests conducted will also be described. Frequency and type of tests

performed will be described by type of healthcare provider ordering the test and clinic type. Rates of HIV and STI tests over the first 12 months will be estimated using time-updated univariate Poisson regression for each regimen type (oral vs LA).

People who could benefit from PrEP (Obj 6)

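### The HIV rate planned through study end is censored at 12 months after index, so it can only repeat the 12-month rate

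*Protocol*

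**What the plan says.** Objective 3 asks for the frequency and rate of HIV diagnoses after PrEP initiation. The synopsis and section 7.7.1.1 call for two horizons: rates "within 12 months of start and through study end will be estimated using time-updated univariate Poisson regression". Annex Tables 9 and 10 give each horizon its own block, and Table 10 has separate person-years and a confidence interval for each.

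Section 7.3.2 (PrEP users, incident HIV diagnosis) lists the two windows as "Within the first 12 months after index PrEP start" and "Through study end (Analysis #1: 30JUN2024; Analysis #2: 30JUN2025". One list follows for both, opening with "Follow-up (FU) will be censored at first of" and naming HIV diagnosis, death, study end, loss to follow-up and "12 months after index date".

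Table 1 in section 7.1 gives the Objective 2-5 censoring criteria for Analysis #1 as "Death, loss to follow-up (12 months after last clinical contact), study end (30JUN2024), 12 months after index date". The Analysis #2 entry differs only in the study-end date. The index date is "Start of first PrEP regimen during the study period".

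For Objective 6, section 7.3.2 repeats both windows and the same list, and it also starts the first window at PrEP start.

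**The concern.** A rule that takes the earliest of several events is unconditional. With a 12-month item in the list, nobody contributes time or a diagnosis after month 12, whatever the rate is called. The protocol thus requires a longer-horizon result and also states a rule that prevents it. Nothing in the document confines the 12-month item to the 12-month rate.

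Within each analysis, the study-end rate is the only HIV rate by PrEP type that extends beyond the first year. That matters most for CAB LA, the small group. Exposure is time-updated, but the clock runs from the first regimen in the study period. Someone who starts on oral PrEP and moves to CAB LA loses CAB LA time to the cap, and a switch more than 12 months after index contributes no CAB LA time and no CAB LA diagnosis.

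The Objective 6 text has the same contradiction, and it anchors follow-up to PrEP start in people who by definition are not on PrEP.

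**Working it through.** The protocol states no figure on this point, so there is none to reproduce. The check is date arithmetic.

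**Inputs**
- Inclusion (section 7.2.1): "Analysis #1: between 21DEC2021 and 30JUN2023"; Analysis #2 runs from 21DEC2021 to 30JUN2024.
- Study end (section 7.3.2, Table 1): 30JUN2024 and 30JUN2025.
- Cap (section 7.3.2, Table 1): 12 months after index.

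**Are the two rates identical?** Under the written rule, administrative follow-up is min(study end − index, 12 months). The last possible index date is 30JUN2023 in Analysis #1 and 30JUN2024 in Analysis #2. Adding 12 months gives exactly the study-end date in each case, and any earlier index date reaches 12 months sooner. Checked date by date, study end precedes index + 12 months for 0 of 557 possible index dates in Analysis #1 and 0 of 923 in Analysis #2. The study-end item is therefore never the deciding one. Events and person-years are the same for both windows, and so are the rates. This result needs no assumption about entry or event rates.

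**How much follow-up is lost?** Assume that index dates are uniform over the window and ignore death, loss to follow-up and HIV diagnosis.

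| | Analysis #1 | Analysis #2 |
|---|---|---|
| Length of inclusion window (days) | 556 | 922 |
| End of inclusion to study end (days) | 366 | 365 |
| Range of potential follow-up (days) | 366 to 922 | 365 to 1,287 |
| Mean potential follow-up (days) | 366 + 556/2 = 644 | 365 + 922/2 = 826 |
| Share discarded by the cap | 1 − 365/644 = 0.433 | 1 − 365/826 = 0.558 |
| Ratio of log-rate CI widths | √(644/365) = 1.33 | √(826/365) = 1.50 |

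The last row also assumes a constant event rate. The standard error of a log rate is then proportional to 1/√events, and expected events are proportional to person-time.

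**Objective 6.** The objective in section 6, the analysis text in section 7.7.1.1 and Annex Tables 34 and 35 all use a 12-month horizon only. Table 1 sets the index at the first OPERA visit with a PrEP indication. The study-end window and the PrEP-start anchor in section 7.3.2 agree with none of these.

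**The case against.** The strongest reply is that the intention is obvious. The synopsis, section 7.7.1.1, Annex Tables 9 and 10 and the Figure 1 footnotes (potential follow-up to 30JUN2024 and 30JUN2025) all point to a longer window. An analyst would notice two identical blocks, and because the data are secondary nothing is lost for good. On this view the list merely lacks a qualifier. It is true that the intention can be inferred and that the data are recoverable. But the cap is written in both the outcome definition and the design table, so an analyst must either report duplicates or depart from the protocol. Section 7.8 asks for documented evidence that the protocol was correctly interpreted and executed, and conflicting text cannot support that.

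Three narrower objections limit the claim:
- Analysis #2 adds a year of inclusion, so CAB LA person-time grows between analyses even under the cap.
- Diagnoses after month 12 drop out of Objective 3 but can still be counted under Objectives 1 and 1a, which give no rate by PrEP type.
- The percentages describe all initiators. Section 7.5 puts CAB LA at 384 of 22,234 first formulations (2%), and other CAB LA users switched to it later. Uniform entry is unsupported for that group, and late switchers could lose proportionally more.

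The Objective 6 wording is a lesser matter, since Table 1 already defines the correct index.

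**Conclusion.** Wrong as written, and it must be corrected before analysis. Applied literally, the censoring rule makes the study-end HIV rate equal to the 12-month rate in both analyses, so one of the two planned Objective 3 rates does not exist. That follows from the dates alone.

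The amount lost, 43% and 56% of potential person-time, rests on uniform entry. Given that, these are upper figures: death, HIV diagnosis and loss to follow-up shorten the uncapped time, and section 7.4 gives an average OPERA follow-up of 1.2 years. The interval-width factors of 1.33 and 1.50 also need a constant rate. None of these figures should be read as an estimate for CAB LA alone.

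**What to change.** In section 7.3.2 (PrEP users), replace the single list with two. For the 12-month rate, keep the present list. For the study-end rate, censor at the first of HIV diagnosis, death, loss to follow-up or study end, and omit the 12-month item. Make the same distinction in the Objective 2-5 row of Table 1, stating that the 12-month item does not apply to the study-end HIV rate. Table 1 should also list HIV diagnosis for the HIV rates, as section 7.3.2 does.

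For Objective 6, delete the study-end window from section 7.3.2 and start the 12-month window at the index visit defined in Table 1. While editing, reconcile the censoring lists (Table 1 includes PrEP initiation, section 7.3.2 does not). Also remove the references to the start of a PrEP type from Annex Tables 33 and 35, and the oral PrEP column heading from Table 35.

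The cost is a wording amendment. The data already in scope run to study end, and the shells of Annex Tables 9 and 10 need no change.

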ANNEX 1 TABLES

Table shells for Analysis #1 are presented. Tables will be identical for Analysis #2, with the exception that study periods will be updated.

Table 1. Identification of the population of people without HIV in OPERA (Analysis #1)

	Included N (%)	Excluded N (%)
All individuals in OPERA		
≥1 clinical encounter between 01JAN2021 and 31DEC2021		
≥18 years old at first clinical encounter in 2021		
No evidence of HIV diagnosis before the first clinical encounter in 2021 [2021 pop]		
≥1 clinical encounter between 01JAN2022 and 31DEC2022		
≥18 years old at first clinical encounter in 2022		
No evidence of HIV diagnosis before the first clinical encounter in 2022 [2022 pop]		
≥1 clinical encounter between 01JAN2023 and 31DEC2023		
≥18 years old at first clinical encounter in 2023		
No evidence of HIV diagnosis before the first clinical encounter in 2023 [2023 pop]		

Table 2. Annual HIV incidence among people without HIV (Analysis #1)

	People without HIV, N	Incident HIV, ^a n (%)
2021		
2022		
2023		

^a New HIV diagnosis or positive HIV test (RNA, antigen/antibody)

Table 3. PrEP use among people with incident HIV (Analysis #1)

	People with incident HIV ^a N =
Never received PrEP, n (%)	
Ever received PrEP, n (%)	
Total number of days on PrEP, median (IQR) ^b	
Number of PrEP formulations received	
1, n (%)	
2, n (%)	
3, n (%)	
Any gaps between formulations, n (%) ^c	
Duration of gaps between formulations, median (IQR)	
PrEP use within ≤12 months before/on HIV diagnosis, n (%)	
Oral PrEP, n (%)	
TDF/FTC, n (%)	
TAF/FTC, n (%)	
CAB LA, n (%)	
Past PrEP use >12 months before HIV diagnosis, n (%)	
Oral PrEP, n (%)	
TDF/FTC, n (%)	
TAF/FTC, n (%)	
CAB LA, n (%)	

^a New HIV diagnosis or positive HIV test (RNA, antigen/antibody)

^b Including all formulations; gaps without PrEP do not count toward the total number of days on PrEP

^c Gap ≥31 days after oral PrEP, gap ≥37 days after first CAB LA injection, or gap ≥67 days after 2nd or subsequent CAB LA injection

Table 4. Identification of the PrEP users population

	Included N (%)	Excluded N (%)
All individuals in OPERA		
Ever received a PrEP prescription/injection in OPERA while HIV negative		
Start a new PrEP formulation (TDF/FTC, TAF/FTC, CAB LA) ^a between 21DEC2021 and 30JUN2023		
≥18 years old at start of index PrEP regimen		

^a Switch from one formulation to another or return to the same formulation after a pause ≥61 days without PrEP

Table 5. PrEP formulations used among PrEP users

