	PrEP users
PrEP formulation at index, N	
Oral, n (%)	
TDF/FTC, n (%)	
TAF/FTC, n (%)	
CAB LA, n (%)	
Switch from oral to CAB LA PrEP within 12 months of initiating index oral PrEP, n (%)	
Switch from CAB LA to oral PrEP within 12 months of initiating index CAB LA, n (%)	

Table 6. Demographic characteristics at start of PrEP regimen^a among PrEP users

	Oral PrEP N=	CAB LA PrEP N=
Age		
Median (IQR)		
18-29		
30-39		
40-49		
50-59		
≥60		
Sex		
Female		
Male		
Unknown		
Transgender, n (%) ^b		
Race		
Black		
Asian		
White		
Mixed or Other races		
Unknown race		
Hispanic ethnicity		
US Region		
Northeast		
South		
Midwest		
West		
US Territories		
Marital status		
Single		
Married/Domestic Partner		
Widowed		
Separated/divorced		
Unknown		
Payer ^c		
Medicaid		
Medicare		
Commercial Insurance		
Other		
Unknown		

^a Individuals who switched PrEP type during follow-up are included in both groups

^b Gender identity is not reported by all clinics and physicians; available data may be insufficient to infer cisgender identity.

^c Payer categories are not mutually exclusive.

Table 7. Clinical care characteristics at start of PrEP regimen^a among PrEP users

	Oral PrEP N=	CAB LA PrEP N=
Months since first OPERA visit, median (IQR)		
Any visits with OPERA provider within 12 months prior to start, n (%)		
Number of visits, median (IQR)		
Prescriber specialty, n (%)		
Infectious diseases		
General practice		
Other		
Unknown		
Clinic type, n (%)		
Healthcare center		
Wellness center		
Other		

^a Individuals who switched PrEP type during follow-up are included in both groups

Table 8. Sexual health characteristics at start of PrEP regimen^a among PrEP users

	Oral PrEP N=	CAB LA PrEP N=
History of STI (ever)		
Syphilis		
Gonorrhea		
Chlamydia		
Chancroid		
Lymphogranuloma venereum		
Mycoplasma genitalium		
Herpes Simplex-2		
Trichomoniasis		
Human papilloma virus/genital warts		
History of STI (past 3 months)		
Syphilis		
Gonorrhea		
Chlamydia		
Chancroid		
Lymphogranuloma venereum		
Mycoplasma genitalium		
Herpes Simplex-2		
Trichomoniasis		
Human papilloma virus/genital warts		

^a Individuals who switched PrEP type during follow-up are included in both groups

Table 9. Incident HIV^a within 12 months of index and through study end among PrEP users

	Oral PrEP N=	CAB LA PrEP N=
Within 12 months of index		
HIV diagnosis, n (%)		
Months from start of PrEP type to HIV diagnosis, median (IQR)		
Negative HIV test within 2 weeks before/on start of PrEP type, n (%)		

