Through study end		
HIV diagnosis, n (%)		
Months from start of PrEP type to HIV diagnosis, median (IQR)		
Negative HIV test within 2 weeks before/on start of PrEP type, n (%)		

^a Incident HIV is only counted for the PrEP type used at the time of diagnosis

Table 10 Incidence rate of HIV^a within 12 months of index and through study end among PrEP users

	Oral PrEP N=	CAB LA PrEP N=
Within 12 months of index		
HIV diagnosis, n (%)		
Person-years of follow-up		
IR per 100 py (95% CI)		
Through study end		
HIV diagnosis, n (%)		
Person-years of follow-up		
IR per 100 py (95% CI)		

^a Incident HIV is only counted for the PrEP type used at the time of diagnosis

Table 11. Oral PrEP coverage within 12 months of index among **oral** PrEP users

	Oral PrEP N=
Mean # pills prescribed (SD)	
Median # of pills prescribed (IQR)	
Mean days of follow-up on oral PrEP ^a (SD)	
Median days of follow-up on oral PrEP ^a (IQR)	
Mean % access (total pills prescribed/days of follow-up) (SD)	
Median % access (total pills prescribed/days of follow-up) (IQR)	

^a If index PrEP is oral: shortest of (a) days from index to first CAB LA injection or (b) 12 months after index; if index PrEP is CAB LA injections: shortest of (a) days from start of switch to oral PrEP to study end or (b) 12 months after index

Table 12. CAB LA PrEP coverage within 12 months of index among CAB LA PrEP users

	CAB LA PrEP N=
Mean days covered ^a (SD)	
Median days covered ^a (IQR)	
Mean days of follow-up on CAB LA PrEP ^b (SD)	
Median days of follow-up on CAB LA PrEP ^b (IQR)	
Mean % coverage (days covered/days of follow-up) (SD)	
Median % coverage (days covered/days of follow-up) (IQR)	

^b Total days between injections, up to 37 days between the first 2 injections or up to 67 days between subsequent injections

^a If index PrEP is oral: shortest of (a) days from index to first CAB LA injection or (b) 12 months after index; if index PrEP is CAB LA injections: shortest of (a) days from first CAB LA injection to study end or (b) 12 months after index

Table 13. Incidence rate of HIV testing events within 12 months of index among PrEP users^a

	Oral PrEP N=	CAB LA PrEP N=
Total # HIV testing events within 12 months of index, n		
Person-years of follow-up		
IR per 100 py (95% CI)		

^a HIV testing events are only counted for the PrEP type used at the time of diagnosis

Table 14. Frequency and type of HIV testing among PrEP users^a

	Oral PrEP N=	CAB LA PrEP N=

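### Chart review of potential HIV cases in Obj 2-5 and Obj 6 is specified only on records from the flag date onward, leaving out the earlier records that best show whether HIV pre-dated index

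*Protocol*

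**What the plan says.** In Protocol section 7.3.2 the outcome for PrEP users is defined by any one of three triggers: "Frequency of new HIV diagnosis and/or detectable HIV RNA and/or positive antigen/antibody test". Confirmation then follows: "All potential HIV acquisitions will be subject to a thorough chart review for confirmation". The line beneath sets out the material for that step, namely the laboratory, diagnosis, ART and note records that OPERA holds "on or after the potential HIV acquisition was identified will be reviewed". The same two lines appear again in section 7.3.2 for Obj 6.

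For Obj 1, section 7.3.2 says "All potential incident HIV diagnoses will be subject to a thorough chart review for confirmation" and names no window.

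Other provisions touch on the same question:

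- Section 7.2.1 requires HIV-negative status for Obj 2-5 and Obj 6. The attrition shell for PrEP users (Annex Table 4) has the row "Ever received a PrEP prescription/injection in OPERA while HIV negative".
- Section 7.7.1.1 says for Obj 3: "The timing of HIV testing relative to PrEP start and HIV diagnosis will be described". The stated aim is to assess attribution to the correct PrEP type.
- Annex Table 9 has the row "Negative HIV test within 2 weeks before/on start of PrEP type, n" (%), and the footnote to Annex Tables 9 and 10 says "Incident HIV is only counted for the PrEP type used at the time of diagnosis".

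**The concern.** The endpoint is an incident diagnosis, so confirming a case involves two questions: is this HIV, and is it new since index? Records from the flag onward answer the first well. The second rests mainly on what came before: the last negative test, an indeterminate result, ART prescribed without a coded diagnosis, or a note that the person was already in HIV care elsewhere. A reviewer who follows the text as written need not open any of those.

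A pre-existing infection that slips past entry could therefore be confirmed and counted as incident, on PrEP under Obj 3 or off PrEP under Obj 6. The CAB LA group is small, so its rate is the one that a single such case would move visibly.

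**Working it through.** The protocol states no figure on this point, so the check is first a comparison of its provisions and then an illustration of size.

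**1. The review windows.** Obj 1: none stated. Obj 2-5 and Obj 6: flag date onward. The same event in the same person can thus be adjudicated on different records under Obj 1 and Obj 3.

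**2. What the entry criterion catches.** A coded HIV diagnosis, detectable RNA or positive antigen/antibody test before index should fail the HIV-negative criterion. If any of these first appears after index, it is itself the flag, because any one of them is enough. What remains is ART without a coded diagnosis, indeterminate results, and free-text notes of earlier HIV care. Neither section 7.2.1 nor Annex Table 4 says which test or look-back establishes HIV-negative status, so nothing in the text guarantees that this remainder is caught at entry.

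**3. Obj 6 is less protected.** Section 7.2.1 requires HIV-negative status, but the attrition shell in Annex Table 28 has no such step: it goes from encounter to age, indication and no PrEP use. Annex Table 1, for Obj 1, does have a row for no earlier HIV diagnosis. Annex Table 35 asks for a negative test relative to the start of a PrEP type, in a population not on PrEP, so that row has no reference date.

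**4. Whether the descriptive items change the count.** The test-timing description and the Annex Table 9 row use earlier tests. Neither is tied to a rule that removes or reclassifies a case.

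**5. Size (illustration only).**

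- Inputs from section 7.5: 767 CAB LA users as stated. The listed components give 384 + 292 = 676, which does not match; both values lie within the range used here. Oral users: 12,110 + 9,740 = 21,850.
- Assumptions: a mean of one year per CAB LA user gives 767 person-years, and a mean of half a year gives 767 × 0.5 = 383.5. For oral users, one year each gives 21,850.
- Added rate per wrongly counted case = 100 / person-years.
 - CAB LA: 100 / 767 = 0.13; 100 / 676 = 0.15; 100 / 383.5 = 0.26 per 100 person-years.
 - Oral: 100 / 21,850 = 0.005 per 100 person-years.
- Exact Poisson 95% limits, 100 × χ²(0.025; 2x) / (2·PY) and 100 × χ²(0.975; 2x+2) / (2·PY), where x is the number of cases and PY the person-years:

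| CAB LA person-years (assumed) | 1 case | 2 cases |
|---|---|---|
| 767 | 0.13 (0.00 to 0.73) | 0.26 (0.03 to 0.94) |
| 676 | 0.15 (0.00 to 0.82) | 0.30 (0.04 to 1.07) |
| 383.5 | 0.26 (0.01 to 1.45) | 0.52 (0.06 to 1.88) |

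The case counts are hypothetical. Where the true count is one, one wrongly counted case doubles the CAB LA estimate, although the intervals overlap widely.

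**The case against.** The strongest reply has four parts.

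**The text does not say 'only'.** It promises a thorough review and then lists records; it does not bar earlier ones. That is true. But a list with a stated start date will be read as the window, and the Obj 1 text shows that the authors could leave the window out.

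**Most earlier evidence is caught already.** The entry criterion and the any-one-of trigger deal with most coded diagnoses and positive results, and notes written after the flag may recount earlier history. This stands, and it narrows the point to the remainder in step 2. A reader might infer that the review cannot establish incidence at all; the documents do not support anything that absolute.

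**PrEP type does not depend on chart review.** A reader might also infer that the window leaves the review unable to assign a case to oral or LA PrEP. That does not follow. Type is a time-updated exposure (section 7.3.1), a case is counted for the type in use at diagnosis, and the test-timing description that serves attribution carries no such window.

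**A strict remedy would do harm.** Counting only cases with a documented earlier negative would turn incident diagnosis into documented seroconversion. The main rate would then depend on testing history, which is likely to differ between PrEP users, for whom section 5 cites required testing before initiation, and the Obj 6 population. This also stands, and the change proposed here avoids it.

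Detailed classification rules may sit in an analysis plan that is not at hand. The window itself, however, is fixed in the protocol.

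**Conclusion.** The point holds in a limited form. For Obj 2-5 and Obj 6 the protocol fixes a review window that omits the records best able to show that HIV pre-dated index, and no other provision fully makes up for it. The entry criterion gives partial protection, less securely for Obj 6.

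The size is about 0.13 to 0.26 per 100 person-years on the CAB LA rate for each wrongly counted case, and about 0.005 on the oral rate. These values rest on assumed person-years, and the documents give no basis for predicting how many such cases there will be. Through study end, longer follow-up would make the increment per case smaller. The conclusion is that the case confirmation step should be improved at almost no cost; it is not that the planned rates are invalid.

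**What to change.** - In section 7.3.2, for both Obj 2-5 and Obj 6, change the review window to records before, on and after the date the potential acquisition was flagged.
- State that a case whose earlier records show HIV before index is excluded from the incident count.
- Keep cases with no documented prior negative test in the main rate. Show them on a separate row, or as a sensitivity analysis, in Annex Tables 9, 10 and 35.
- Add an HIV-negative step to Annex Table 28, and give the negative-test row in Annex Table 35 a reference date that exists for people not on PrEP, such as the Obj 6 index date.

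The cost is a wording change in two places, small edits to the table shells, and a somewhat longer review of charts that are already being opened.
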